3 STUDY POPULATION AND STUDY PROCEDURES

4.1 Inclusion and exclusion criteria, justification of study population

We will recruit 20 healthy subjects and comprise two study visits with at least 24 hours between the two visits. Participants will be subjected to minimally distressing tests and intervention procedures. Participants will be included in this study according to the following criteria:

Inclusion criteria:

- Healthy adult volunteers
- German speaking, or good knowledge of the German language
- Able to understand the study
- Able to give informed consent

Exclusion criteria:

- Regularly taking medication potentially interfering with pain sensation (analgesics, antihistamines and calcium and potassium channel blockers)
- Current pregnancy
- Daily smokers (as per WHO definition: A daily smoker is someone who smokes any tobacco product at least once a day.)
- Neuropathy
- Chronic pain (> 3 Months)

- Neuromuscular or psychiatric disease
- Known or suspected heart, kidney or liver disease
- Hypertension (Systolic (mmHg) >130, Diastolic (mmHg) >80)
- History of fainting or seizures
- History of Frostbite
- Current medications (psychoactive medication, narcotics, intake of analgesics) or being currently in psychological or psychiatric treatment.

4.2 Recruitment, screening and informed consent procedure

Participants will be recruited from the University campus/Hospital of Basel by word of mouth, flyers and via advertisement on the homepage of the University of Basel and social media. A minimum of 24 hours between recruitment procedure and decision of participant to participation is given. Due to the study design, the participants cannot be informed about all aspects of the procedure before the start of the study. Therefore, at the first Visit (randomly A or B), the investigators will explain to each participant the nature of the study as described in IC 1 (see appendix 2). Further, the procedures involved will be explained, the expected duration, the potential risks and benefits and any discomfort they may entail. The participants then sign IC 1. IC 1 will be signed and dated by the investigator or his designee at the same time as the participant sign. No medical records will be screened for this study.

Participants will receive CHF 100 for their participation in both study visits. After maximum 6 months or in case of withdrawal, the participants will be debriefed about the true aim of the study and sign IC 2 (see appendix 2) which they will receive via post. A copy of the signed informed consents will be given to the study participant. The consent forms will be retained as part of the study records.

4.3 Study procedures

The overall study duration will be: Recruitment start date: 01.10.2021, Study completion: 28.02.2023. The study comprises two visits (A and B) of 60 minutes each at the Breath Analysis laboratory of [name] (UKBB). The breath analysis platform consists of a commercially available ion source (FIT, Spain) coupled to a high-resolution mass spectrometer (Thermo Scientific, Bremen). The process is completely non-invasive as the participant just exhales through a commercially available disposable bacterial/viral filter coupled to the ion source.

4.4 Withdrawal and discontinuation

We foresee the following reason for participants not to complete the study:

- Technical failure of the SESI-MS Ionization analytical platform
- Withdrawal of informed consent

In the case of withdrawal, the mass spectra and any material of the participant will be destroyed or deleted. In the case of drop-outs, we will replace the participants.

4 STATISTICS AND METHODOLOGY

5.1. Statistical analysis plan and sample size calculation

This is a pilot study and no literature has been found on the topic of placebo and metabolomics that may allow for a reasonable sample size estimation. Thus, we employ a rule of thumb approach based on our experiences in previous metabolomics studies (Pablo Sinues, 2013). (Pablo Sinues Tarokh L, 2014)

All 20 participants will undergo two study visits. The order in which they will receive differs, with participants being randomly split into two groups via matlab randi function: 10 participants first CPT + placebo and then CPT, and 10 participants vice versa. Null and alternative hypotheses are formulated as follows:

- Null hypothesis: the mean difference concentration (i.e. signal intensity as proxy) of exhaled metabolites is equal in CPT and in CPT+placebo ($\mu_{CPT} = \mu_{CPT+Placebo}$)
- Alternative hypothesis: the mean difference concentration (i.e. signal intensity as proxy) of exhaled metabolites is significantly different in CPT and in CPT+ placebo ($\mu_{CPT} \neq \mu_{CPT+Placebo}$)

A two-way repeated measures ANOVA will be performed to evaluate the effect of different treatments (CPT and CPT + placebo) over time on exhaled metabolite abundance. False discovery rate for multiple testing will be taken care using established procedures (Storey, 2002). The preprocessing of the raw mass spectra and the statistical analysis will be implemented using MATLAB (MathWorks, Massachusetts, US).

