3.3 Study design

Single center; national, implemented at the University Children's Hospital Basel (UKBB). Randomized Crossover design; Pilot Study.

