5.2. Handling of missing data and drop-outs

This is a pilot study looking at physiological outcomes, thus it will be analyzed on a perprotocol basis. In the case of drop-outs, we will simply replace the participants.

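### Independent MATLAB randi draws do not guarantee the stated 10/10 sequence split, the sequence of replacements is left open, and the named ANOVA has no period term to absorb an imbalance

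*Protocol*

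**What the plan says.** Section 3.3 gives the design as "Randomized Crossover design; Pilot Study". Section 5.1 states that "All 20 participants will undergo two study visits" and then names both the mechanism and the result in one sentence: "participants being randomly split into two groups via matlab randi function: 10 participants first CPT + placebo and then CPT, and 10 participants vice versa". It mentions no permutation, block, cap or redraw that would turn random integers into a fixed split. Section 4.2 adds only that the first visit is A or B at random.

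The analysis named in section 5.1 is a two-way repeated measures ANOVA of treatment over time. It names no period or sequence term.

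On drop-outs, section 4.4 says "In the case of drop-outs, we will replace the participants" and section 5.2 says "In the case of drop-outs, we will simply replace the participants". Neither says whether the replacement takes over the vacated sequence or is allocated afresh. Of the analysis, section 5.2 says that "it will be analyzed on a perprotocol basis".

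**The concern.** A two-sequence crossover is given equal arms so that a difference between first and second visit cancels out of the treatment contrast. Here such a difference is plausible, because the same painful test is repeated, possibly only 24 hours later (section 4.1). With no period term in the named model, balance is the only stated protection against it.

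The function named does not provide that balance by itself: randi, as generally understood, returns independent uniform integers drawn with replacement. The protocol has gone beyond leaving the method open. It fixes a method that, used plainly, usually misses the result it promises. One allocation serves every m/z feature, so an unlucky split affects all of them in the same trial, and false discovery rate control does not remove a bias of that kind.

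**Working it through.** **Inputs.** N = 20, target 10/10, mechanism randi, model treatment by time (all section 5.1); drop-outs replaced (sections 4.4 and 5.2). *Assumptions:* randi is called once per participant as an independent fair draw between two sequences (the call is not shown), and the size of any visit-order effect (the protocol gives none).

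**1. Does the mechanism reproduce 10/10?** The number in one sequence is Binomial(20, 0.5).

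- P(10/10) = C(20,10)/2^20 = 184,756/1,048,576 = 0.176, so the stated split is missed with probability 0.824.
- Two-sided tails:

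| Split | P(this or worse) |
|---|---|
| 12:8 | 0.503 |
| 13:7 | 0.263 |
| 14:6 | 0.115 |

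If randi is instead used to pick ten of the 20 participant numbers, all ten are distinct with probability 20!/(10! × 20^10) = 0.065. Redrawing the whole list until it is balanced does give 10/10, after 1/0.176 ≈ 5.7 attempts on average.

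**2. What an uneven split does to the contrast.** Let τ be the treatment effect and π the shift from first to second visit. The within-person difference (placebo visit minus CPT visit) has mean τ − π in the n1 participants with placebo first and τ + π in the n2 with placebo second. Averaged over 20 people this is τ + π(n2 − n1)/20. The fraction of π that enters is:

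- 12:8: 4/20 = 0.20
- 13:7: 6/20 = 0.30
- 14:6: 8/20 = 0.40

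**3. Error rate of a nominal 5% test without a period term.** This uses an unadjusted paired t test as a stand-in for the treatment comparison, 200,000 simulated trials, and assumed π of 0.5 and 1 SD of the within-person difference.

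| Split | π = 0.5 SD | π = 1 SD |
|---|---|---|
| 10:10 | about 3% | about 0.6% |
| 12:8 | 4.5% | 3.0% |
| 13:7 | about 6.5% | about 7.5% |
| 14:6 | about 10% | about 16% |
| Averaged over the binomial split | 5.0% | 5.0% |

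The low rates at 10:10 arise because the unmodelled period shift swells the residual variance. Balance without a period term therefore leaves the test conservative.

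**4. Cost of imbalance if period is modelled.** The variance is proportional to 1/n1 + 1/n2. Relative to 10/10 it is 1.04 at 12:8, 1.10 at 13:7 and 1.19 at 14:6, and the bias in step 2 is gone.

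**5. Replacements.**

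- Exact 10/10 start, each replacement drawn afresh, one drop-out: balance survives with probability 0.50.
- Same start, two drop-outs: both come from one sequence with probability 9/19 and one from each with probability 10/19. So P = (9/19)(1/4) + (10/19)(1/2) = 0.38.
- Start from plain independent draws: P(10/10) stays at about 0.176, because completers are still independent fair draws if drop-out is unrelated to sequence.
- Replacement into the vacated sequence: no change in balance.

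**The case against.** The strongest reply is that the protocol fixes the outcome, ten and ten, and merely names the software. Randi can sit inside a scheme that yields that outcome, for example by redrawing until balanced, and the text does not exclude this. A reader might infer that randi cannot produce 10/10. That is too strong: plain draws reach it in 17.6% of cases and a constrained scheme reaches it always. What stands is that no such step is written, so the stated method does not guarantee the stated split.

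A reader might also infer that replacing drop-outs erodes the balance further. The protocol does not support that. If allocation is by independent draws, fresh replacement draws leave the chance of 10/10 where it was. Erosion needs a balanced start together with freshly drawn replacements. The fair point is that the replacement's sequence is unspecified.

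Third, the rates of 10% and 16% might be read as the trial's false-positive rate. They hold only given a 14:6 split and assumed period effects. Over the randomisation as a whole the rate is 5.0%, and at 12:8 it is below nominal.

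Finally, the harm depends on the missing period term, and this is a 20-person pilot in which each participant is their own control. Both facts are right. They lower the severity and show that the remedy must include the model.

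**Conclusion.** The concern holds in limited form. Under plain independent draws the method in section 5.1 misses its own 10/10 split about 82% of the time, and the replacement rule does not protect a 10/10 start if one is obtained. As the only named model lacks a period term, 0.30 of any visit-order effect would enter the placebo contrast at 13:7 and 0.40 at 14:6. Splits at least that uneven have probabilities of 26% and 11.5%.

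This is bias conditional on an uneven draw. It is not inflation of the overall type I error. The conclusion rests on randi being used as one fair draw per participant, on a period effect existing at all, and on the ANOVA being run as named; an analysis plan that adds period would remove the bias and leave only the modest variance cost. For an exploratory pilot this is a should-fix.

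**What to change.** 1. In section 5.1, replace randi with a random permutation (randperm, or permuted blocks so that balance also holds over the recruitment period) of a fixed list of ten A-then-B and ten B-then-A slots.
2. In sections 4.4 and 5.2, state that each replacement takes the sequence slot of the participant replaced.
3. Add period (visit order) to the ANOVA. Steps 1 and 2 alone would leave the test conservative; with period in the model the balanced design is analysed at its correct error rate.

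The cost is one line of code, two protocol sentences and one model degree of freedom. A fixed list does make the last assignments predictable to anyone who keeps count, so it is best held by someone who does not enrol participants.

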3.2 Primary and secondary endpoints

Primary endpoint

The variable of primary interest is the variation of signal intensity of mass-to-charge ratio (m/z) of exhaled metabolites across the conducted CPT pain analgesia-placebo effects trial.

Secondary endpoints

Differentially exhaled metabolites across the pain vs. no-pain measurements. Exhaled metabolites for differences between placebo responders and non-responders. Exhaled metabolites association with blood pressure and heart rate.

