3.4. Study intervention

Visit A (CPT, 60 min)

The participant receives an explanation how this study will work in terms of exhalation maneuvers, medication and CPT and signs informed consent (IC) 1 if this is the first visit. The participant will then be connected to a patient monitor for continuous tracking of heart rate and blood pressure. An exhalation set typically contains six replicate exhalations in positive and negative ion mode. The method is highly standardized, as described in (Singh, Tancev et al. 2019), whereby exhalation maneuvers are controlled by a mass flow controller and guided by CO₂ exhalation. Typical coefficients of variation for such replicate measurements are in the order of 7%. In total, this process takes around seven minutes. First, two baseline exhalations are performed. Then, the CPT is performed according to the 'CPT Guide' (for details, see below Figure 3). This takes around 5min. Directly after the CPT, the proband executes first post-pain exhalations set. Probands then rest 15min and executes the second post-pain exhalations set. In case this is the second visit, probands receive 100CHF. At all times, a medical doctor will be available inside the UKBB premises in case the participant requires medical assistance.

[figure not shown]

Figure 1. Schematic flowchart and process description of the study visit A

Visit B (CPT+Placebo, 60 min)

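### The primary null is written as equality of two overall condition means, so read literally it averages baseline breath into the placebo effect; the deciding ANOVA term is not named

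*Protocol*

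**What the plan says.** Section 5.1 of the protocol gives the null as "the mean difference concentration (i.e. signal intensity as proxy) of exhaled metabolites is equal in CPT and in CPT+placebo" and sets beside it the equation μ_CPT = μ_CPT+Placebo. The alternative is that this quantity "of exhaled metabolites is significantly different in CPT and in CPT+ placebo". Neither has a time index or a baseline term, and the protocol does not say what the *mean difference* is taken from.

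The model follows: "A two-way repeated measures ANOVA will be performed to evaluate the effect of different treatments (CPT and CPT + placebo) over time". The protocol does not say whether the treatment main effect or the treatment-by-time interaction decides the hypothesis. On multiplicity it says "False discovery rate for multiple testing will be taken care using established procedures", without a level.

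The primary endpoint in section 3.2 does not settle the matter: "The variable of primary interest is the variation of signal intensity of mass-to-charge ratio (m/z) of exhaled metabolites across the conducted CPT" names no time point or contrast.

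Section 3.4 gives the measurements within a visit. For Visit A: "First, two baseline exhalations are performed". The CPT follows, then one exhalation set directly afterwards and another after 15 minutes of rest. Visit B is the same procedure with the medication information and the spray added before the CPT. Section 4.1 puts the visits at least 24 hours apart. Section 1.2 states the aim as examining breath before and after the placebo is given.

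**The concern.** In a treatment-by-time layout, equality of the two condition means is the hypothesis of the treatment main effect. Two consequences follow if that is the test.

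First, breath sampled before the spray cannot carry a placebo effect, yet it enters the Visit B mean with the same weight as each post-CPT set. The estimate is then a diluted version of the effect that section 1.2 asks about.

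Second, the visits fall on different days. Any shift in a participant's breath or in the instrument between those days stays in the error of the main effect, although each visit already collects the baseline that could remove much of it.

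The trial has 20 participants and corrects for multiple metabolites, so lost precision matters. If the deciding term stays open, it could also be chosen after the results are seen.

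**Working it through.** **Inputs from the protocol.** There are 20 participants, each measured at both visits (section 5.1), with two post-CPT sets per visit (section 3.4). The number of baseline time points, k, is taken as 1 or 2, because the wording of section 3.4 allows either. The sample size comes from a rule of thumb ("we employ a rule of thumb approach based on our experiences in previous metabolomics studies"), so there is no planned power to reproduce.

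**Assumptions, not in the protocol.** Consider the within-participant visit difference (B minus A) at each time point. Let each have variance 1 and any two have correlation r. The placebo effect δ is present only in the m = 2 post-CPT sets, with δ = 0.6 (in SDs of a visit difference). The test is two-sided at 5% per metabolite before false discovery rate control. Period effects are left out. The 1-df tests use the noncentral t with 18 df throughout, for comparability.

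**Dilution.** The main effect estimates δ × m/(k + m). For k = 1 this is 2/3 × 0.6 = 0.40. For k = 2 it is 1/2 × 0.6 = 0.30.

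**Four tests at k = 1, r = 0.5.**

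- Main effect: variance (1 + 2r)/3 = 2/3; noncentrality 0.40/√(0.6667/20) = 2.19; power 55%.
- Overall interaction (2 and 38 df): the sum of squared deviations of the effects (0, 0.6, 0.6) from their mean is 0.24; λ = 20 × 0.24/(1 − 0.5) = 9.6; power 76%.
- 1-df change contrast (post mean minus baseline): variance (1 + r)/2 + 1 − 2r = 0.75; noncentrality 0.6/√(0.75/20) = 3.10; power 83%.
- Baseline as covariate: variance (1 + r)/2 − r² = 0.75 − 0.25 = 0.50; noncentrality 0.6/√(0.50/20) = 3.79; power 95%.

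**Range over r and k.**

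| k | r | Main effect | Overall interaction | Change contrast | Baseline covariate |
|---|---|---|---|---|---|
| 1 | 0 | 83% | 46% | 55% | 95% |
| 1 | 0.5 | 55% | 76% | 83% | 95% |
| 1 | 0.7 | 47% | 94% | 97% | 99% |
| 2 | 0 | 72% | 57% | 72% | 95% |
| 2 | 0.5 | 36% | 88% | 95% | 98% |
| 2 | 0.7 | 30% | 99% | 100% | 100% |

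At low r the change contrast can do worse than the main effect (55% against 83% at k = 1, r = 0). The covariate analysis is at least as good as the other three in every row.

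**Second check, different model.** A simulation used two baseline and two post-CPT measurements per visit, an effect of 1.0 residual SD, and a participant-by-visit SD of 0, 0.5, 1 or 2 residual SDs. The main effect estimated 0.50 of the true effect, with power 85%, 57%, 27% and 11%. The change contrast held 85% and the 3-df interaction about 73% throughout. Type I error stayed near 5% for all three tests.

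**The case against.** A reader might infer that the plan ignores baseline altogether. The document does not support that. A treatment-by-time ANOVA contains an interaction that uses each visit's own baseline, and where that term is the test the dilution does not occur. *Mean difference* could also mean change within a visit, in which case the null is already baseline-corrected. Naming the deciding term is often left to a statistical analysis plan, and one may exist. All of this stands, and it is why the point is conditional on how the null is read. What remains is that the protocol itself writes out the hypothesis, and the equation it writes is not the interaction.

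A reader might also take the widest gap, 36% against 98%, as the cost of the plan. It is not. It compares the least favourable reading, with two baseline time points, against the best alternative. The interaction in the same setting reaches 88%.

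Dilution in itself need not cost power relative to a change contrast. In the simulation the two are equal (85%) when there is no visit-to-visit variation, and the protocol does not give the size of that variation. Validity is not at stake, since type I error is unaffected.

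The order of baseline and spray in Visit B is inferred from the text, because the visit flowcharts are not available. For the same reason it cannot be inferred that the baseline has fewer replicates than the post-CPT sets: the phrase in section 3.4 may mean breaths or full sets.

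**Conclusion.** The point holds as a defect in how the primary hypothesis is stated. Its literal form is the treatment main effect, which does not match the aim in section 1.2 and shrinks the estimated effect to 2/3 or 1/2, provided that baseline precedes the spray. The alternative reading, the overall interaction, avoids the dilution but spreads the test over several degrees of freedom.

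Under the stated assumptions (k = 1, r = 0.5, effect 0.6 SD), one post-CPT contrast with the same visit's baseline as covariate has about 95% power, against 55% and 76% for the two readings. The direction of this comparison held at all the correlations tabulated, from 0 to 0.7. Its size depends on an effect size and a correlation that the protocol does not give, and in some settings the margin over the interaction is small (99% against 94% at k = 1, r = 0.7). The change is worth making before the data are analysed. It concerns efficiency and clarity, and does not mean that the planned analysis would be invalid.

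**What to change.** In section 5.1, state the primary test as the CPT+placebo minus CPT difference in post-CPT log signal intensity, with the same visit's baseline as a covariate. Prefer this to a plain change-score contrast, which can lose power when the baseline correlation is low. Rewrite the null, the alternative and the term *mean difference* to match, and align the primary endpoint in section 3.2. State in section 3.4 where the baseline falls relative to the medication information and the spray.

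The cost is revised wording, slightly more analysis work and one degree of freedom for the covariate. No additional measurements are needed.

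### The crossover analysis has no period term, so any visit-order effect inflates the error of the placebo contrast and costs power

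*Protocol*

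**What the plan says.** Protocol section 3.3 gives the design as "Randomized Crossover design; Pilot Study". Section 4.1 plans "two study visits with at least 24 hours between the two visits", and section 5.1 confirms that "All 20 participants will undergo two study visits". Section 5.1 intends an even split by order, "10 participants first CPT + placebo and then CPT, and 10 participants vice versa", with "participants being randomly split into two groups via matlab randi function".

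The hypotheses in section 5.1 are two-sided; the alternative is that the signal "is significantly different in CPT and in CPT+ placebo". The only model stated is this: "A two-way repeated measures ANOVA will be performed to evaluate the effect of different treatments (CPT and CPT + placebo) over time". It is applied to exhaled metabolite features, with a false discovery rate procedure on top. Period, sequence and carry-over are not mentioned anywhere in the protocol.

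**The concern.** Randomising the order of visits makes period a design factor, and the stated model leaves it out. From the protocol's own description, a second visit may well differ from a first. The painful immersion is no longer new, and the controlled exhalation manoeuvre has been practised. The gap between visits has a minimum but no maximum.

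If the second visit differs from the first by a period effect, a participant who has CPT alone first shows the placebo effect plus that period effect. A participant who has placebo first shows the placebo effect minus it. A model without period treats this systematic plus-or-minus difference as random noise between people. The placebo contrast then has too large a standard error. The p-values passed to the false discovery rate step are also no longer uniform under the null, for any feature that has a visit-order effect.

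**Working it through.** **Inputs.** From the protocol: n = 20 with two visits each, 10/10 by order, a two-sided question (section 5.1), and three measurement times per visit, taken as baseline, directly after the CPT and after the rest (section 3.4). Assumed, because the protocol gives no figure: a two-sided 5% level per feature, a placebo effect tau = 0.66 SD (chosen to give about 80% power) and a period effect pi of 0.25, 0.5 or 1.0 SD. SD means the standard deviation of the within-person difference, net of period, and is set to 1.

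The protocol has no power figure to reproduce: for the sample size, "we employ a rule of thumb approach based on our experiences in previous metabolomics studies".

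**Treatment main effect.** In a two-way repeated measures ANOVA this test is the paired t-test on D, the person's mean with placebo minus the mean without.

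- n1 participants with CPT alone first: D = tau + pi + e
- n2 participants with placebo first: D = tau − pi + e
- Bias of the mean of D: pi(n1 − n2)/n
- Expected variance without a period term: 1 + pi² × (4·n1·n2/n)/(n − 1)

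At 10/10 the bias is 0 and the variance is 1 + (20/19)pi². Rejection rates follow by integrating over the noncentral chi-square distribution of the sum of squares; simulation agrees to within about half a point.

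| pi (assumed) | Variance factor | Type I error | Power |
|---|---|---|---|
| 0 | 1.00 | 5.0% | 79.9% |
| 0.25 | 1.07 | 4.4% | 78.0% |
| 0.5 | 1.26 | 2.9% | 72.2% |
| 1.0 | 2.05 | 0.6% | 49.4% |

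With a period term (18 instead of 19 degrees of freedom), type I error is 5.0% and power 79.7% for every pi. If pi = 0, the term therefore costs 79.9 − 79.7 = 0.2 points (0.3 in simulation).

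**Treatment-by-time test.** This was simulated with three times per visit, independent errors with SD 1 for the difference at each time, and a placebo effect of 0.8 at the two later times. At 10/10:

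- No period effect: type I error 5.0%, power 71%.
- Constant shift of the whole visit by 1 SD: unchanged, because the shift cancels.
- Visit-order change of 1 SD in the two post-CPT values only: type I error 2.0%, power 56%.

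**Unequal split.** At 12/8 the bias is pi × 4/20, or 0.05, 0.10 and 0.20 SD for the three values of pi. At 13/7 it is pi × 6/20, or 0.075, 0.15 and 0.30 SD. Type I error of the main effect without a period term, for pi = 0.25, 0.5 and 1.0:

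- 11/9: 4.5%, 3.3%, 1.1%
- 12/8: 4.9%, 4.5%, 3.0%
- 13/7: 5.5%, 6.5%, 7.5%

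Up to 12/8 the inflated variance outweighs the bias. If randi is used as 20 independent draws (an assumption), the exact binomial probabilities are 17.6% for 10/10, 50.3% for 12/8 or worse and 26.3% for 13/7 or worse.

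**The case against.** The strongest reply is that under the stated 10/10 allocation the omission creates no bias and no excess of false positives. It only makes the test conservative, in a pilot whose size was never based on power. That is correct, and it limits how serious the point is.

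The period effect is also an assumption. At 0.25 SD the loss is about two points of power, and the largest value shown exceeds the assumed placebo effect itself. This stands too; the figures are a range, not an estimate.

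The phrase about treatments over time may point to the interaction as the main test, and each visit has its own baseline. On that reading a constant visit shift does no harm. But the protocol does not say which test is primary, and a changed response to the second CPT would affect both.

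A separate statistical analysis plan could add the term. Section 5.1 nevertheless commits to a named two-factor model, so the point concerns what is stated and not a detail left open.

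A reader might infer three stronger things that the documents do not support:

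- That the placebo contrast is biased as planned. It is not at 10/10. Bias needs an unequal split, and that depends on how randi is used or on which sequence is given to replacements for drop-outs (sections 4.4 and 5.2). The protocol settles neither.
- That any unequal split raises the false-positive rate. The figures above show this only from about 13/7.
- That leaving out sequence is itself a defect. A pure sequence effect lies between participants and drops out of the within-person contrast. Period is the term that matters.

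**Conclusion.** The point holds as one of efficiency and calibration. The stated model omits a factor that the design creates. At 10/10 the cost ranges from about 2 to 30 points of power for the treatment main effect, for assumed period effects of 0.25 to 1.0 SD, with a type I error below the nominal level. The treatment-by-time test is untouched by a constant visit shift, but it loses about 15 points (71% to 56%) in the assumed case of a 1 SD visit-order change in the CPT response. Bias of pi(n1 − n2)/n is conditional on an unequal realised split.

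The results rest on the assumed effect sizes and a 5% level per feature. The change should be made because it is nearly free, but the omission does not invalidate the planned analysis.

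**What to change.** In section 5.1, replace the two-way ANOVA for each m/z feature by a crossover mixed model. Use fixed effects for treatment, time, treatment-by-time, period and period-by-time (sequence optional), and random effects for participant and for visit within participant.

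For the treatment main effect there are two simple equivalents:

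- Compare visit 1 minus visit 2 between sequences. The expected values are −tau − pi (CPT alone first) and tau − pi (placebo first); they differ by 2·tau, so halve the difference.
- Average the two sequence means of placebo minus no placebo: [(tau + pi) + (tau − pi)]/2 = tau.

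Do not compare placebo minus no placebo between sequences. That gives (tau + pi) − (tau − pi) = 2·pi, which is a test of the period effect. At 10/10 it rejects only 5% of the time when tau = 0.66 and pi = 0, but 56% and 99% of the time when tau = 0 and pi = 0.5 or 1.0.

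The cost is analysis wording and one or two degrees of freedom. The same model removes the bias from an unequal split.

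A period term does not remove carry-over of expectation. If having placebo first shifts the later CPT-alone visit by lambda, D in that sequence becomes tau − pi − lambda, and the average is tau − lambda/2. A first-visit-only estimate can be reported alongside, labelled as descriptive: it compares 10 with 10 participants between persons and has low power.
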